## 5. Study Design

### 5.1. Overall Design

[figure not shown]
This will be a multicenter, double-blind, randomized, placebo-controlled trial. One dose of alvelestat (MPH966), 120 mg bid, will be tested against placebo. These doses are based on PK and PD modelling of alvelestat (MPH966) inhibition of human neutrophil elastase.

The participants will be those patients with the AATD at risk for emphysema (Pi\*ZZ, Pi\*SZ, Pi\*null, or another rare phenotype/genotype known to be associated with either low (serum AAT level <11 µM or <57.2 mg/dL) or functionally impaired AAT including “F” or “I” mutations)

Following a screening period of up to 4 weeks, patients will be dosed with study treatment or placebo for 12 weeks, with a subsequent 4-week follow-up period for safety and determination of the offset of the mechanistic effect of MPH966 on the primary endpoint (desmosine/isodesmosine).

The study is divided into 3 phases: a screening phase, treatment phase, and washout phase as detailed below:

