### 9.4.3. Adverse Events of Special Interest

Some AEs, regardless of their severity or outcome, will be expedited due to the relevance for subject safety or study treatment safety profile. These events should be reported to the DCC within 24 hours, as indicated in [Appendix 4](#). The AESIs for alvelestat (MPH966) are:

- Liver function abnormalities defined as:
  - a) Any occurrence of (i) ALT or AST elevations  $>5 \times \text{ULN}$  or (ii) ALT or AST  $>3 \times \text{ULN}$  and total bilirubin  $>2 \times \text{ULN}$  or INR  $>1.5$  or the appearance of worsening fatigue, nausea, vomiting, RUQ pain/tenderness, fever, rash, or eosinophilia.
  - b) Any occurrence of  $<5 \times \text{ULN}$  or ALT or AST  $<3 \times \text{ULN}$  and total bilirubin  $<2 \times \text{ULN}$  where the tests have been repeated within 48 to 72 hours and the elevation confirmed on at least 2 separate occasions.

For participant safety and to ensure that the hepatotoxic potential of the study treatment to be determined, a standardized procedure for identification, monitoring, and evaluation of liver events must be followed as outlined in [Section 9.3.3](#) and [Section 8.1](#).

- ECG/Cardiac Events

If a study subject experiences any of the following cardiovascular events, the event should be reported immediately as an AESI and the study treatment discontinued:

- a) Absolute QTcF >500 ms or >60 ms increase from baseline.
- b) Any clinically significant cardiac abnormality on ECG.

- Infection

Any new infection that requires the use of systemic antimicrobial treatment (antibiotics, anti-viral, anti-fungal, or anti-mycobacterial) should be investigated with clinically relevant diagnostic tests.

Acute exacerbations of COPD are considered AESI.

- Neutropenia

- a) Absolute neutrophil count less than or equal to  $1.0 \times 10^9/L$  on 2 consecutive repeat tests within 48 to 72 hours.

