# 3.4 General Study Design and Plan

This will be a multicenter, double-blind, randomized, placebo-controlled trial. One dose of Alvelestat (MPH966), 120 mg bid, will be tested against placebo. These doses are based on PK and PD modelling of Alvelestat (MPH966) inhibition of human neutrophil elastase.

The participants will be those patients with the AATD at risk for emphysema (Pi\*ZZ, Pi\*SZ, Pi\*null, or another rare phenotype/genotype known to be associated with either low [serum AAT level <11  $\mu$ M or <57.2 mg/dL] or functionally impaired AAT including "F" or "I" mutations)

Following a screening period of up to 4 weeks, patients will be dosed with study treatment or placebo for 12 weeks, with a subsequent 4-week follow-up period for safety and determination of the offset of the mechanistic effect of MPH966 on the primary endpoint (desmosine/isodesmosine).

The study is divided into 3 phases: a screening phase, treatment phase, and washout phase as detailed below:

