# 4.2 Primary Safety Endpoints

- 1. Numbers and % of subjects who experience at least 1 treatment-emergent adverse event
- 2. Adverse events of special interest (liver function abnormalities, corrected QT interval/cardiac, infections, and neutropenia)

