# 8 Efficacy Analyses

Analyses on all efficacy outcomes will be based on the 12-week period after randomization. Time periods included are baseline, Week 4, Week 8 and Week 12. Safety outcomes will include through Week 16.

Actual values, absolute change in actual values and the relative (percent) change from baseline will be summarised with descriptive statistics for continuous variables overall and by treatment arms. Relative (percentage) change will be calculated by:

[(Week or EndPoint value – Baseline Value) / Baseline value)] x 100%.

Baseline value will be computed as the last non-missing value prior to first study treatment dose at baseline visit (V1).

EndPoint will be computed as:

- Value at Week 12 for the completers (regardless of treatment compliance) or
- EOT value must be last non-missing post-baseline value for those that discontinue treatment before Week 12.

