# 9.3 Safety Outcomes

### 9.3.1 Primary Safety Outcomes

The primary safety outcomes of interest are (1) numbers and % of subjects who experience at least 1 treatment-emergent adverse event and (2) adverse events of special interest (liver function abnormalities, corrected QT interval/cardiac, infections, and neutropenia). AEs will be coded using the Medical Dictionary for Regulatory Activities (MedDRA). Summaries will be by system organ class and preferred term. We will also present data separately by augmentation.

Treatment-emergent AEs (TEAEs) are defined as any AE occurring on or after the first dose of study medication. Listing will be sorted by treatment arm, subject ID, chronologically (start and end dates) and then alphabetically by SOC, PT and then verbatim description. The listing will include all the distinct levels of SOC, PT and the verbatim Investigator description reported in the study. A flag per subject will be included to indicate whether the patient received COVID-19 vaccination. If a participant experiences the same preferred term multiple times, the event will be counted only once overall and by the greatest severity. The frequency and incidence of TEAEs will be presented by system organ class and preferred term for each treatment group (number and percentage of participants experiencing at least 1 AE per preferred term as well as the number of observed events per preferred term). Separate tables will be presented by severity and by relationship to study drug. All AEs will be presented in a comprehensive listing

including participant number, treatment regimen, day of onset, severity, seriousness, action taken, outcome, relationship to treatment, onset/stop, and duration. Details of SAEs and AEs leading to withdrawal will be listed separately.

The frequency and incidence of adverse events of acute exacerbations of COPD will be presented (number and percentage of participants experiencing at least 1 AE per preferred term as well as the number of observed events per preferred term) and overall. Events that started after treatment initiation (TEAEs) up until Week 12 will only be presented, meaning that events commencing after the end of treatment and during the safety follow up period will not be summarized.

AESIs, including liver function abnormalities, ECG/cardiac events, infections, and neutropenia, will be tabulated and summarized by treatment group and overall.

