Overall Summary of Adverse Events	Safety Set (SAF)
Summary of Treatment Emergent Adverse Events (TEAEs) by System Organ Class and Preferred Term	Safety Set (SAF)
Summary of Treatment Related Treatment Emergent Adverse Events (TEAEs) by System Organ Class and Preferred Term	Safety Set (SAF)
Summary of Serious Treatment Emergent Adverse Events (TEAEs) by System Organ Class and Preferred Term	Safety Set (SAF)
Summary of Treatment Related Serious Treatment Emergent Adverse Events (TEAEs) by System Organ Class and Preferred Term	Safety Set (SAF)
Summary of Treatment Emergent Adverse Events (TEAEs) Leading to Permanent Withdrawal of Study Drug by System Organ Class and Preferred Term	Safety Set (SAF)
Summary of Adverse Events of Special Interest (AESIs) by System Organ Class and Preferred Term	Safety Set (SAF)
Summary of Adverse Events Leading to Death by System Organ Class and Preferred Term	Safety Set (SAF)
Summary of Treatment Emergent Adverse Events (TEAEs) by System Organ Class, Preferred Term and Maximum Intensity	Safety Set (SAF)
Summary of Adverse Events of Acute Exacerbations of COPD up until Week 12 by System Organ Class and Preferred Term	Safety Set (SAF)
Deaths, Listing	Safety Set (SAF)

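### The dedicated COPD exacerbation table stops at Week 12 although the SAP runs safety through Week 16, and its cut-off is unclear for participants who stop drug early

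*SAP*

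**What the plan says.** SAP 9.3.1 plans a separate summary of acute COPD exacerbations: participants and events per preferred term, and overall. It sets the window in one sentence with two halves. The first half reads "Events that started after treatment initiation (TEAEs) up until Week 12 will only be presented". The second half explains that "events commencing after the end of treatment and during the safety follow up period will not be summarized". The table title in SAP 14.1 repeats the limit: "Summary of Adverse Events of Acute Exacerbations of COPD up until Week 12 by System Organ Class and Preferred Term".

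Other parts of the plan point to a longer window:

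- SAP 8, as a general rule: "Safety outcomes will include through Week 16".
- Protocol 5.1 has 12 weeks of dosing "with a subsequent 4-week follow-up period for safety and determination of the offset of the mechanistic effect of MPH966 on the primary endpoint", and SAP 3.4 repeats this. Safety is thus one stated purpose of the off-drug period.
- Protocol 9.4.1 collects adverse events from consent to the follow-up visit, and the Schedule of Activities has adverse event recording at Week 16.
- Protocol 9.4.3, under the infection heading: "Acute exacerbations of COPD are considered AESI". AESIs are a primary safety endpoint (SAP 4.2 and 9.3.1).
- SAP 9.3.1 defines a treatment-emergent adverse event (TEAE) by a start point, the first dose, with no end date. Its AESI sentence has no cut-off either.

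**The concern.** The SAP sets a general safety window to Week 16 and then, for an event type that the protocol singles out, uses a shorter one without giving a reason. Protocol 10.3.2 has no Week 12 limit on TEAEs or AESIs, and SAP 10, which lists departures from the protocol, does not mention this one.

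Two things are at stake. First, the washout is where an exacerbation after stopping drug would show, and the table built to show exacerbations by arm leaves that period out. One exacerbation at Week 14 could count in the TEAE and AESI tables and be absent from the exacerbation table, so a reader would meet different counts for the same event type.

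Second, the sentence treats Week 12 and end of treatment as the same boundary. They differ for anyone who stops drug early, because SAP 6.2 defines the end-of-treatment visit to include premature discontinuation and Protocol 8.1 says that stopping treatment does not by itself mean leaving the study. Two programmers could then build different tables from the same text.

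**Working it through.** The plan states no figure for this point, so there is nothing to reproduce. The check compares the windows and adds simple arithmetic.

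**1. Share of follow-up outside the table, treatment completer.** Inputs: dosing to Week 12, last visit at Week 16 (Protocol 5.1 and Schedule of Activities; SAP 3.4).

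- Excluded: 16 − 12 = 4 weeks.
- Share: 4/16 = 25%.

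**2. Early stopper.** Take a participant who stops drug at Week 4, stays in follow-up, and has an exacerbation at Week 7.

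- First half of the SAP 9.3.1 sentence (up to Week 12): the event is included.
- Second half, with both conditions applied (after end of treatment and also in the safety follow-up period): Week 7 is after end of treatment but before the Week 12 to 16 phase. The event is not excluded, and the two halves agree.
- Second half, read on end of treatment alone: the event is excluded, and the two halves disagree.

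On that last reading the excluded share is (16 − 4)/16 = 12/16 = 75%. On the other two it is 4/16 = 25%, as for a completer. The 75% also assumes that the participant is followed to Week 16.

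**3. Where a Week 14 exacerbation would appear.**

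- TEAE tables by system organ class and preferred term: yes, by arm, since the TEAE definition has no end date.
- AESI table: it should appear, by arm, because Protocol 9.4.3 makes it an AESI. The lists in SAP 4.2 and 9.3.1 name liver, cardiac, infection and neutropenia events but not exacerbations, so inclusion rests on the protocol.
- Listings in SAP 14.3: yes, in the listing of all adverse events and in the one for COPD or exacerbation of COPD, whose title has no Week 12 limit.
- Dedicated exacerbation table: no.

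The TEAE and AESI tables are laid out by preferred term. Only the dedicated table is described as giving an overall exacerbation figure as well.

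**4. Illustration of size.** The documents give no exacerbation rate. As an assumption, take 0.5 to 2 per patient-year, constant over time, with everyone followed. Expected events in the omitted window = participants per arm × 4 × 7/365.25 × rate.

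- 30 per arm (the completer target): 2.30 patient-years, so about 1.2 to 4.6 events per arm, out of about 4.6 to 18.4 over 16 weeks.
- 33 per arm (the randomized target): 2.53 patient-years, so about 1.3 to 5.1 events per arm, out of about 5.1 to 20.2.

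These counts only show the order of size; the conclusion does not depend on them.

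**The case against.** The strongest case for the plan is that this is one supplementary table, openly labelled, and that the omitted events are reported elsewhere. TEAEs have no end date, the AESI table has no cut-off, and the listings show each event with treatment and day of onset. An on-treatment window is also a legitimate display: Protocol 9.4.5 equates five half-lives with 4 days, so most of Weeks 12 to 16 is off drug. Safety results are descriptive (SAP 9), so no test or decision rule depends on the choice.

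Most of this stands, and it rules out two stronger readings that a reader might infer.

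- *Post-treatment exacerbations are never compared between arms, or the primary safety endpoint is truncated.* The documents do not support this. The TEAE and AESI tables carry these events by arm without a Week 12 limit.
- *The table penalizes tolerability: the arm with more early stops loses more time at risk, up to 75% for a Week 4 stopper.* This follows only if the condition about the safety follow-up period is dropped from the SAP sentence. With both conditions kept, an event before Week 12 stays in, and no such dependence arises.

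The objection does not remove the conflict with SAP 8 or the loss of washout events from the one overall exacerbation count. Nor does it supply a stated rule for early stoppers, or a SAP statement that exacerbations are in the AESI table.

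**Conclusion.** The point holds as a minor correction. The only table giving an overall exacerbation count by arm omits the washout, which is 25% of collected follow-up for a treatment completer, against the SAP's own Week 16 rule and without a stated reason. The 25% rests only on the visit schedule. The effect on event counts cannot be stated, because the documents give no rate.

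The wording for early stoppers should be tightened because it can be read two ways, not because it is shown to bias the comparison. That the omitted events are still counted by arm elsewhere assumes that the AESI table follows the protocol definition and that the TEAE tables follow the SAP definition as written.

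**What to change.** In SAP 9.3.1, replace the windowing sentence with a rule along these lines: acute exacerbations of COPD will be summarized by arm in the Safety Set, as participants and events, from first dose to Week 16, and split by onset into on treatment (first to last dose) and after last dose to Week 16. The split settles where an early stopper's event belongs and keeps the on-treatment view.

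In the same section, state that exacerbations are included in the AESI table, as Protocol 9.4.3 requires, with the same onset window. Retitle the SAP 14.1 table so that it no longer stops at Week 12.

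The cost is SAP wording and one extra table panel. No new data are needed and no clinical rule changes. The small downside is that the total includes off-drug time, which the split shows separately.

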### 9.3.2 Secondary Safety Outcomes

For secondary safety outcomes,

- Physical examination results will be listed by subject ID and body system. ECG parameters will be summarized as observed values and change from baseline by treatment group and study visit.
- Abnormal findings ("normal", "abnormal, not clinically significant", and "abnormal, clinically significant") will be summarized by the number and percentage within each category and change from baseline will be summarized by shift tables.
- Laboratory parameters will be summarized as observed values and change from baseline by treatment group and study visit.
- Vital signs (temperature, SBP, DBP, heart rate, respiration rate, oxygen saturation) and ECG results will be summarized as observed values and change from baseline by treatment group and study visit.

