#### Liver Test Abnormalities

The following monitoring schedule is proposed when a case of acute liver function abnormalities or worsening of a liver function abnormality is reported:

- If ALT or AST are between 1.5 to 3 × ULN, regular monitoring (every 2 weeks at a minimum) is required until event resolution and patient can **continue on study treatment** during this period.
- If ALT or AST are  $\geq 3 \times$  ULN, repeat the test within 48 to 72 hours and the **study treatment will be temporarily discontinued** while awaiting repeat tests results; if the repeat tests is again  $\geq 3 \times$  ULN or  $\geq 2 \times$  pre-treatment level, testing needs to be repeated at least twice weekly until event resolution or a return to baseline value while the study treatment is **withheld**.
- If AST or ALT are  $\geq 5x$  ULN, a repeat value should be obtained within 24-48 hours. If the repeat ALT and AST values is  $\geq 5 \times$  ULN, the drug should be discontinued and the patient followed until the laboratory values normalize or stabilize, in addition to initiating potential (Drug Induced Liver Injury) DILI evaluation.

Discontinue Alvelestat (MPH966) for the following hepatic adverse events:

- Regardless of the magnitude of the transaminase elevation, if the bilirubin is elevated (any level) in addition to the presence of signs and symptom(s) such as rash, eosinophilia, nausea, vomiting, or right upper quadrant pain,
- INR  $\geq 1.5$  and TB  $\geq 2x$  ULN, irrespective of the magnitude of ALT or AST elevation.
- TB elevation  $\geq 2x$  ULN, and ALP  $\geq 2x$  ULN for cholestatic liver injury.

For each scenario, initiate potential DILI evaluation for alternative etiologies and obtain a hepatology consult. Liver biopsy should be considered for DILI. The complete liver profile including PT/INR must be repeated within 48-72 hours after first abnormal value is obtained. Follow the patient until laboratory parameters stabilize or normalize. Study medication can be restarted only if an alternative etiology is “definitively” identified and liver tests have returned to baseline. Testing for alternative etiologies can include serology tests (hepatitis A, hepatitis B, hepatitis C, Cytomegalovirus (CMV), Epstein-Barr Virus (EBV), Herpes Simplex Virus (HSV), varicella zoster virus (VZV), parvovirus, toxoplasmosis), imaging, and pathology assessments (creatinine phosphokinase, clotting) as appropriate to the clinical situation.

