## **9. Study Assessments and Procedures**

- Study procedures and their timing are summarized in the SOA.
- Adherence to the study design requirements, including those specified in the SOA, is essential and required for study conduct.
- All screening evaluations must be completed and reviewed to confirm that potential participants meet all eligibility criteria. The Investigator will maintain a screening log to record details of all participants screened and to confirm eligibility or record reasons for screening failure, as applicable.
- .
- Sample handling: Routine bloodwork and laboratory measurements used for safety monitoring and eligibility assessment (CMP, coagulation measurements, CBC, pregnancy testing, etc.) will be processed and measured using local laboratory. Samples (blood, sputum, BAL) used for PK or biomarker assessment will undergo initial processing at the local site but will be shipped to a central lab ([name]) at UAB for curation and analysis. The procedure is detailed in the MOP.
- Repeat or unscheduled samples may be taken for safety reasons or for technical issues with the samples.
- Biomarker samples (blood, sputum, and BAL) will be stored for up to 60 months after the end of the study.

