	
Vital signs will be summarized as observed values and change from baseline by treatment group and overall.
 
Physical Examination Physical examination results will be listed by subject ID and body system.
 
ECG ECG parameters will be summarized as observed values and change from baseline by treatment group and study visit.
 
Abnormal findings (“normal”, “abnormal, not clinically significant”, and “abnormal, clinically significant”) will be summarized by the number and percentage within each category, and change from baseline will be summarized by shift tables.
 
Clinical Laboratory Laboratory parameters will be summarized as observed values and change from baseline by treatment group and study visit.
 
Values outside the normal range will be summarized by the number and percentage within each category, and change from baseline will be summarized by shift tables.
 
Safety and PK Relationships The safety correlation analysis with drug concentration may be done for the safety parameters shown to be sensitive to alvelestat exposure. The comparison of exposure will be done between groups with non-clinically significant changes and clinically significant changes in safety parameters using graphic and statistical methods where data allow.

Exploratory	The details will be described in the SAP finalized before database lock.

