# Statistical Analysis Plan

# ATALANTa Study

Table		
Number	Table Name	Analysis Set
	Summary of Hematology Laboratory Parameters	Safety Set (SAF)
	Summary of Clinical Chemistry Laboratory Parameters	Safety Set (SAF)
	Summary of Urinalysis Laboratory Parameters	Safety Set (SAF)
	Summary of Vital Sign Parameters	Safety Set (SAF)
	Summary of Electrocardiogram (ECG) Parameters	Safety Set (SAF)
	Summary of Study Drug Compliance	Safety Set (SAF)

1	4.	21	Lis	ting	of	Figures	
---	----	----	-----	------	----	---------	--

Figure Number	Figure Name	Analysis Set
	Mean (± SE) Absolute Values and % Change from	Full Analysis Set (FAS)
	Baseline in Plasma Desmosine/Isodesmosine at Scheduled Study Visits	
	Individual Absolute Values in Plasma	Full Analysis Set (FAS)
	Desmosine/Isodesmosine at Scheduled Study Visits	
	Mean (± SE) Absolute Values and % Change from	Per-Protocol Set (PPS)
	Baseline in Plasma Desmosine/Isodesmosine at	
	Scheduled Study Visits	
	Individual Absolute Values in Plasma	Per-Protocol Set (PPS)
	Desmosine/Isodesmosine at Scheduled Study Visits	
	Mean (± SE) Absolute Values and % Change from	Full Analysis Set (FAS)
	Baseline in Plasma Aa-Val-360 at Scheduled Study Visits	
	Individual Absolute Values Plasma Aa-Val-360 at Scheduled Study Visits	Full Analysis Set (FAS)
	Mean (± SE) Absolute Values and % Change from	Full Analysis Set (FAS)
	Baseline in Serum NE activityat Scheduled Study	
	Visits	
	Individual Absolute Values in Blood Serum NE	Full Analysis Set (FAS)
	activityat Scheduled Study Visits	
	Mean (± SE) Absolute Values and % Change from	Full Analysis Set (FAS)
	Baseline in Plasma proteinase 3 levels at	
	Scheduled Study Visits	
	Individual Absolute Values in Plasma proteinase 3	Full Analysis Set (FAS)
	levels at Scheduled Study Visits	
	Mean (± SE) Absolute Values and % Change from	Full Analysis Set (FAS)
	Baseline in Plasma cathepsin B levels at Scheduled	
	Study Visits	
	Individual Absolute Values in Plasma cathepsin B	Full Analysis Set (FAS)
	levels at Scheduled Study Visits	
	Mean (± SE) Absolute Values and % Change	Full Analysis Set (FAS)
	from Baseline in Plasma CRP levels at	
	Scheduled Study Visits	
	Individual Absolute Values in Plasma CRP levels at	Full Analysis Set (FAS)
	Scheduled Study Visits	
	Mean (± SE) Absolute Values and % Change	Full Analysis Set (FAS)
	from Baseline in Plasma IL-6 at Scheduled Study	
	Visits	
	Individual Absolute Values in Plasma IL-6 at	Full Analysis Set (FAS)
	Scheduled Study Visits	

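### SAP 9.3.2 omits, without declaring it, the protocol's out-of-range counts and (on its natural reading) shift tables for laboratory data, so abnormalities that do not become an AE or AESI have no planned by-arm count

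*SAP*

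**What the plan says.** Protocol 10.3.2, under Clinical Laboratory, plans three displays. The first is observed values and changes by arm and visit. The second is a count of abnormal results: "Values outside the normal range will be summarized by the number and percentage within each category". The third is a shift display: "change from baseline will be summarized by shift tables".

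SAP 9.3.2 gives laboratory data one bullet: "Laboratory parameters will be summarized as observed values and change from baseline by treatment group and study visit". A separate bullet on abnormal findings says these "will be summarized by the number and percentage within each category and change from baseline will be summarized by shift tables". That bullet names no parameter.

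SAP 14.1 lists "Summary of Clinical Chemistry Laboratory Parameters" and "Summary of Hematology Laboratory Parameters" but no out-of-range or shift table. SAP Section 10 records changes on augmentation, on spirometry, sputum and BAL, and on the primary model. It records nothing on laboratory displays.

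Safety bloods "will be processed and measured using local laboratory" (Protocol 9; Appendix 2 agrees).

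**The concern.** Safety and tolerability is a primary objective, and liver abnormality and neutropenia are named AESIs. The protocol's own liver history is told in threshold counts: 14 instances of ALT or AST at or above 3 × ULN in the COPD studies (Protocol 5.7). Its liver monitoring and stopping rules (Protocol 8.1) and its liver AESI definition (Protocol 9.4.3) are written in multiples of ULN.

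The SAP should therefore let a reader ask how many participants in each arm crossed a limit, using the laboratory data themselves. As written it plans no such count. At stake is a modest excess of transaminase rises or low neutrophil counts on active treatment that never reaches the AE or AESI tables. It would be visible only to someone who counts through the listings.

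**Working it through.** No figure in the plan underlies this point, so the first check compares the two documents.

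**1. Displays planned for laboratory data**

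| Display | Protocol 10.3.2 | SAP 9.3.2 | SAP 14.1 | Declared in SAP 10 |
|---|---|---|---|---|
| Observed and change, by arm and visit | yes | yes | one summary table each for chemistry and hematology | not needed |
| Number and % out of range | yes | absent | none | no |
| Shift from baseline | yes | only in the bullet that names no parameter | none | no |

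The unnamed bullet follows the ECG sentence and uses the three categories (normal; abnormal without and with clinical significance) that the protocol gives under ECG. ECG is the natural reading. The SAP does not say so.

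**2. Which abnormal results still reach a by-arm table**

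| Result | Route under the SAP |
|---|---|
| ALT/AST >5 × ULN | AESI |
| ALT/AST >3 × ULN with bilirubin >2 × ULN, INR >1.5 or listed symptoms | AESI; ALT ≥3 × ULN with raised bilirubin or INR is also an SAE (Protocol Appendix 2) |
| ALT/AST 3–5 × ULN, no symptoms, confirmed on repeat | probably AESI part (b), but its limits are written as upper bounds only, so this depends on how a site reads it |
| ALT/AST 3–5 × ULN, no symptoms, not confirmed | AE only if judged clinically significant |
| ALT/AST 1.5–3 × ULN | as above; Protocol 8.1 requires monitoring at least every 2 weeks, not a 48–72 h confirmation |
| Neutrophils ≤1.0 × 10⁹/L on two consecutive repeats | AESI |
| Neutrophils below normal but above 1.0 × 10⁹/L | AE only if judged clinically significant |

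Three rows rest on clinical judgement alone. SAP 4.5.4 and Protocol Appendix 4 set aside findings attributed to the underlying disease unless they are worse than expected. Protocol 5.8 states that 49% of adult Pi*ZZ patients have small ALT increases. A rise on treatment could therefore reasonably be put down to AATD.

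**3. What the continuous summary shows**

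If k of n participants in an arm rise from baseline b to peak p at one visit, the arm mean moves by k(p − b)/n. Inputs: n = 30 to 33 (Protocol 10.1; SAP 3.5.3). Baseline b = 0.5 to 1.5 × ULN is an assumption, with its upper end at the entry limit in exclusion criterion 6.

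- One participant to 3 × ULN: (3 − 1.5)/33 = 0.045 to (3 − 0.5)/30 = 0.083 × ULN.
- One participant to 5 × ULN: (5 − 1.5)/33 = 0.106 to (5 − 0.5)/30 = 0.150 × ULN.
- Three participants to 3 × ULN: 3(3 − 1.5)/33 = 0.136 to 3(3 − 0.5)/30 = 0.250 × ULN. As a count this is 3/33 = 9.1% to 3/30 = 10.0%.

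In raw units, one participant going from 25 to 150 U/L (assumed values) moves the mean by 125/33 = 3.8 U/L, or 125/30 = 4.2 U/L.

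The maximum is also planned and would show the 150. It would not show how many participants crossed a limit. High maxima at three visits could be one participant or three.

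**4. Raw units against ULN rules**

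The documents give no local ULNs. A value of 150 U/L is 150/40 = 3.75 × ULN if the ULN is 40. It is at or above 3 × ULN only where the local ULN is 50 or less (150/3), and at or above 5 × ULN only where it is 30 or less (150/5). A pooled U/L maximum cannot be placed against the protocol's cut-points without the local range.

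**The case against.** The strongest reply is that the plan already covers the events that matter, and much of it stands. A reader might infer four stronger things, none of which the documents support.

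- *That only visit means remain.* SAP 6.1 gives minimum, maximum, median and quartiles for continuous data and plans listings of all data by site, treatment and subject. SAP 14.3 adds listings of participants with clinically significant chemistry or hematology values.
- *That liver and neutrophil risks cannot be seen by arm.* SAP 9.3.1 tabulates both AESIs by treatment group.
- *That the comparison rests wholly on what investigators choose to report.* The AESI definitions contain numeric limits, and Protocol Appendix 2 requires possible Hy's law cases to be reported as SAEs.
- *That a peak found at an unscheduled repeat disappears from the by-visit tables.* The instruction to "repeat the test within 48 to 72 hours" is triggered by a value already at or above 3 × ULN. If that value came from a scheduled draw, it is in the table.

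Two further replies are fair. SAP 14.1 lists no ECG shift table either, so its titles alone do not prove a display was dropped. SAP 9.3.2 is also silent on unscheduled values and on ULN scaling, and silence is not a decision to exclude them.

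These replies leave the middle of the range untouched. Results that fall short of an AESI and are not judged clinically significant have no planned count by arm, and listings are not an arm comparison.

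**Conclusion.** The point holds as a reporting inconsistency between protocol and SAP that should be corrected. It is not a loss of the safety signal. The out-of-range counts are missing from SAP 9.3.2. The laboratory shift tables are missing if the unnamed bullet is about ECG, as its categories indicate. Neither omission is declared.

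The consequence is limited to abnormalities that do not become an AE or AESI: ALT/AST of 1.5–3 × ULN, unconfirmed symptom-free ALT/AST of 3–5 × ULN, and neutrophils below normal but above 1.0 × 10⁹/L. For these, a group that makes up 9–10% of an arm can sit behind a mean shift of 0.14–0.25 × ULN.

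That size rests on the assumed baseline range and on all three rises falling at one visit; spread over visits, each visit's shift would be smaller. The comparison of the two documents rests on no assumption beyond the reading of the one bullet.

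**What to change.** - In SAP 9.3.2 and 14.1, restore the laboratory out-of-range counts and percentages and the shift tables, by arm, with shifts taken from baseline to worst post-baseline value.
- Base them on each local laboratory's normal range, with ALT and AST in multiples of the local ULN at the protocol's existing cut-points of 1.5, 3 and 5.
- State that unscheduled values count towards the worst value.
- State which parameters the abnormal-findings bullet covers.
- If the omission was intended, declare and justify it in SAP Section 10 instead.

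The worst-value and ULN-multiple details go beyond what Protocol 10.3.2 literally promised. They are what make its counts readable against its own rules.

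The cost is some SAP wording and a few extra tables from results already collected. Local ULNs must be in the database; the documents do not say whether they are, so that needs checking. No visit, sample or clinical rule changes.
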